6.3. Secondary Efficacy Endpoints

6.3.1. Definition of Secondary Efficacy Endpoints

The secondary endpoints of this study are as follows:

- 1) Proportion of subjects who have progression to cirrhosis by Week 48
- 2) Proportion of subjects who have a ≥ 1 -stage improvement in fibrosis (according to the NASH CRN classification) without worsening of NASH at Week 240
- 3) Proportion of subjects who have a ≥ 1 -stage improvement in fibrosis (according to the NASH CRN classification) at Week 48 and Week 240
- 4) Proportion of subjects who have NASH resolution (defined as lobular inflammation of 0 or 1 from at least 1 at baseline and hepatocellular ballooning reduced to 0 from at least 1 at baseline; both criteria are necessary conditions) without worsening of fibrosis (according to the NASH CRN classification) at Week 48 and Week 240

6.3.2. Analysis of the Secondary Efficacy Endpoints

For the secondary efficacy endpoints, the stratified MH test defined for the primary histology efficacy endpoint in Section 6.1.3 will be used to compare the differences in proportions between SEL 18 mg (SEL 6 mg) and placebo, adjusting for the presence or absence of diabetes mellitus at baseline and ELF test score ≥ 9.76 or < 9.76 at baseline. The point estimates, 95% CIs and corresponding p-values based on a Z test for the differences in proportions, and 95% CIs for proportion of responder in each treatment group based on the Clopper-Pearson method will be calculated.

A logistic regression analysis will also be performed to assess the odds ratio between each of the SEL arms and the placebo arm, adjusting for stratification factors. The point estimates of odds ratios, 95% CIs of odds ratios, and corresponding p-values for each SEL arm versus placebo arm will be reported.

Forest plots of the treatment differences in proportion of subjects who achieved a response for each secondary efficacy endpoint will be generated for subgroup analyses as described in Section 3.4 and sensitivity analyses as described in Section 3.6.1, respectively.

The point estimates and 95% CIs based on stratified MH tests of NRI data will be provided in the subgroup analysis for the primary histology endpoint and secondary endpoints. The point estimates and 95% CIs based on a proportional hazard model will be provided for the subgroup analysis for the primary clinical efficacy endpoint. When the grouping variable is identical to one of the stratification factors (ie, subgroups by baseline diabetes status or baseline ELF category), this stratification factor will not be adjusted in the modeling.

6.4. Exploratory Efficacy Endpoints

6.4.1. Definition of Exploratory Efficacy Endpoints

CCI
[Redacted text block containing multiple lines of blacked-out content]

CCI

[Redacted text block containing multiple lines of blacked-out content]

CCI [Redacted]

[Redacted]

[Redacted]

[Redacted]

[Redacted]

[Redacted]

[Redacted]

[Redacted]

[Redacted]

[Redacted]

[Redacted]

[Redacted]

[Redacted]

[Redacted]

[Redacted]

6.4.2. Analysis Methods for Exploratory Efficacy Endpoints

CCI [Redacted]

[Redacted]

CCI
[Redacted]

[Redacted]

[Redacted]

[Redacted]

[Redacted]

[Redacted]

[Redacted]

[Redacted]

[Redacted]

[Redacted]

[Redacted]

[Redacted]

[Redacted]

6.5. Change From Protocol-Specified Efficacy Analyses

The analyses for the objective to determine whether noninvasive measures of fibrosis can predict histological regression and/or progression of fibrosis and clinical complications of cirrhosis will be included in the statistical analysis plan for noninvasive tests.

7. SAFETY ANALYSES

Subjects will be grouped as defined in Section 3.2.

7.1. Adverse Events and Deaths

7.1.1. Adverse Event Dictionary

Clinical and laboratory AEs will be coded using the current version of MedDRA. SOC, HLG, HLT, PT, and LLT will be provided in the AE dataset.

7.1.2. Adverse Event Severity

Adverse events are graded by the investigator as Grade 1, 2, 3, 4, or 5 according to Common Terminology Criteria for Adverse Events (CTCAE). The severity grade of events for which the investigator did not record severity will be categorized as “missing” for tabular summaries and data listings. The most severe grade will be considered in data summary if a subject experienced multiple events under the same category. The missing category will be listed last in summary presentation when applicable.

7.1.3. Relationship of Adverse Events to Study Drug

Related AEs are those for which the investigator selected “Related” on the AE CRF to the question of “Related to Study Treatment.” Relatedness will always default to the investigator’s choice, not that of the medical monitor. Events for which the investigator did not record relationship to study drug will be considered related to study drug for summary purposes. However, by-subject data listings will show the relationship as missing.

7.1.4. Serious Adverse Events

Serious adverse events (SAEs) will be identified and captured as SAEs if AEs met the definitions of SAEs that were specified in the study protocol. Serious adverse events captured and stored in the clinical database will be reconciled with the SAE database from Gilead Pharmacovigilance and Epidemiology before data finalization.

7.1.5. Treatment-Emergent Adverse Events

7.1.5.1. Definition of Treatment-Emergent Adverse Events

Treatment-emergent adverse events (TEAEs) for the Randomized/OL Phase are defined as 1 or both of the following:

- Any AEs with an onset date on or after the study drug start date and no later than 30 days after permanent discontinuation of study drug in the Randomized Phase (and before the first dosing date in the OL Phase)/ OL Phase.
- Any AEs leading to premature discontinuation of study drug in the Randomized/OL Phase.

7.1.5.2. Definition of Adverse Events > 30 Days Posttreatment

Adverse events > 30 days posttreatment for the Randomized/OL Phase are defined as any AEs with an onset date later than 30 days after permanent discontinuation of study drug in the Randomized Phase (and before the first dosing date in the OL Phase)/ OL Phase.

7.1.5.3. Incomplete Dates

If the onset date of an AE is incomplete and the AE stop date is not prior to the first dosing date of study drug, then the month and year (or year alone if month is not recorded) of onset determine whether an AE is treatment emergent in the corresponding treatment phase. The event is considered treatment emergent if both of the following 2 criteria are met:

- The AE onset is the same as or after the month and year (or year) of the first dosing date of study drug, and
- The AE onset date is the same as or before the month and year (or year) of the date corresponding to 30 days after the date of the last dose of study drug in the Randomized Phase (and before the first dosing date in the OL Phase)/OL Phase.

An AE with completely missing onset and stop dates, or with the onset date missing and a stop date later than the first dosing date of study drug, will be considered to be treatment emergent. In addition, an AE with the onset date missing and incomplete stop date with the same or later month and year (or year alone if month is not recorded) as the first dosing date of study drug will be considered treatment emergent. In above cases if an AE is considered treatment-emergent, it will not be considered > 30 days posttreatment.

7.1.6. Summaries of Adverse Events and Deaths

Treatment-emergent adverse events and AEs > 30 days posttreatment will be summarized for the Safety Analysis Set/OL Safety Analysis Set according to the subject grouping defined in Section 3.2.

The number and percentage of subjects who experienced at least 1 TEAE will be provided and summarized by SOC, HLT and PT. For other AEs described below, summaries will be provided by SOC and PT:

- TEAEs by severity grade
- TEAEs of Grade 3 or higher (by maximum severity)
- TEAEs of Grade 2 or higher
- All TE treatment-related AEs
- TE Treatment-related AEs of Grade 3 or higher (by maximum severity)

- TE Treatment-related AEs of Grade 2 or higher
- All TE SAEs
- All TE treatment-related SAEs
- All TE treatment-related AEs by severity grade
- Death
- All TEAEs leading to discontinuation of study drug In the Randomized Phase, TEAEs leading to discontinuation of study drug include 2 categories: protocol-specified clinical events, and TEAEs leading to premature discontinuation of study drug. The latter will be provided in a separate summary table.

A brief, high-level summary of AEs described above (except for the summary by severity grade) will be provided by treatment group and by the number and percentage of subjects who experienced the above AEs. All deaths observed in the study and subjects who completed randomized study drug due to protocol-specified clinical events will be also included in this summary.

Multiple events will be counted only once per subject in each summary. Adverse events will be summarized and listed first in alphabetic order of SOC and HLT within SOC (if applicable), and then in descending order of PTs by frequency in the (OL) SEL 18 mg group within each SOC or HLT in the Randomized/OL Phase. For summaries by severity grade, the most severe grade will be used for those AEs that occurred more than once in an individual subject in the Randomized/OL Phase.

In addition to the above summary tables, the following tables will be summarized by PT only, in descending order of frequency in the (OL) SEL 18 mg group for the Randomized/OL Phase:

- All TEAEs
- TEAEs of Grade 3 or higher (by maximum severity)
- TEAEs of Grade 2 or higher
- TE treatment-related AEs
- TE Treatment-related AEs of Grade 3 or higher (by maximum severity)
- TE Treatment-related AEs of Grade 2 or higher
- All TESAEs
- All TE treatment-related SAEs

The following tables for AEs > 30 days posttreatment will be summarized by PT only, in descending order of frequency in the (OL) SEL 18 mg group for Randomized/OL Phase:

- All AEs > 30 days posttreatment
- Treatment-related AEs > 30 days posttreatment
- SAEs > 30 days posttreatment

A brief, high-level summary of AEs > 30 days posttreatment described above will be provided by treatment group and by the number and percentage of subjects who experienced the above AEs.

In addition, data listings will be provided for the following:

- All AEs, indicating whether the event is treatment emergent
- All AEs of Grade 3 or higher
- SAEs
- Deaths
- AEs leading to discontinuation of study drug

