Once the clinical event (except histological progression to cirrhosis, all-cause mortality and liver transplantation) is confirmed by the Hepatic Events Adjudication Committee, the subject will no longer participate in the Randomized Phase and will be offered the option to receive SEL 18 mg in the OL Phase for a total treatment duration of 240 weeks inclusive of the Randomized Phase.

Rollover into the OL Phase of the study must occur within 60 days of confirmation of the event. Subjects starting the OL Phase of the study will complete the same study procedures as during the Randomized Phase of the study, starting with the Day 1 visit with the exception of the liver biopsy **CCI**

**CCI** Hepatic clinical events will be adjudicated and deaths will be reviewed by the Hepatic Events/DILI Adjudication Committee only during the Randomized Phase of the study; potential DILI events and cardiovascular events including deaths will continue to be adjudicated in the OL Phase by the Hepatic Events/DILI Adjudication Committee and the Cardiovascular Events Adjudication Committee, respectively.

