### 6.7. Open-Label Phase

Subjects who progress to cirrhosis on liver biopsy or experience a hepatic clinical event (refer to Section 3.2) prior to completing the Week 240 Visit of the Randomized Phase will be offered the option to rollover into an Open-Label (OL) Phase of the study. Each of the clinical events (except death and liver transplantation) will require confirmation by a Hepatic Events Adjudication Committee. All deaths will be reviewed by this committee to determine if they are liver-related.

Subjects who undergo liver transplantation are not eligible to participate in the OL Phase of the study and should discontinue from the study immediately. Subjects who have permanently discontinued study drugs are not eligible for the OL Phase of the study.

Once a clinical event (except histological progression to cirrhosis, death and liver transplantation) is confirmed by the Hepatic Events Adjudication Committee, the subject will no longer participate in the Randomized Phase and will be offered the option to receive SEL 18 mg in the OL Phase for a total treatment duration of 240 weeks inclusive of the Randomized Phase.

Rollover into the OL Phase of the study must occur within 60 days of confirmation of the event. Subjects starting the OL Phase of the study will complete the same study procedures as during the Randomized Phase of the study, CCI

. Hepatic clinical events will be adjudicated and deaths will be reviewed by the Hepatic Events/DILI Adjudication Committee only during the Randomized Phase of the study; potential DILI events and cardiovascular events including deaths will continue to be adjudicated in the OL Phase by the Hepatic Events/DILI Adjudication Committee and the Cardiovascular Events Adjudication Committee, respectively.

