1.3. Sample Size and Power

With a sample size of 320 subjects in each active treatment arm and 160 subjects in the placebo arm, the study has 94% power to detect a difference in the proportion of subjects with a ≥ 1 -stage improvement in fibrosis without worsening of NASH of 15% or more at Week 48 at a significance level of 0.025 (2-sided), assuming the proportion of subjects that meet the endpoint in the placebo arm is 12%.

With regard to the clinical efficacy endpoint, subjects will be followed for a period of up to 240 weeks. The estimate of the expected event rate is 30% in untreated patients, producing an expected EFS rate of 70% at 240 weeks in the placebo arm. SEL is expected to improve the EFS rate to 83.7% (expected event rate of 16.3%) compared with placebo (hazard ratio (HR), 0.50). We also expect a 20% overall dropout rate. Given the above assumptions, for comparison of the SEL arms versus the placebo arm, together with a total sample size of 800 subjects (2:2:1 ratio), and assuming the log-rank test statistic is evaluated using a 2-sided 0.025 significance level, the study will have 85% power to evaluate the superiority of each SEL arm versus placebo with respect to EFS.

Therefore, the overall power for the trial, assuming independence between the primary efficacy endpoint and clinical efficacy endpoint, is 80% ($94\% \times 85\%$). It should be noted that this is a lower bound estimate as these 2 endpoints are expected to be positively correlated.

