3.2. Subject Grouping

For analyses based on the FAS, subjects will be grouped according to the treatment to which they were randomized. For analyses based on the Safety Analysis Set, subjects will be grouped according to actual treatment received. The actual treatment received will differ from the randomized treatment only when the actual treatment differs from the randomized treatment for the entire treatment duration. In this case, the actual treatment received is defined as the treatment received for the entire treatment duration.

For safety analyses, subjects will be grouped into the following:

Randomized Phase (only Randomized Phase data will be summarized for these groups)

- 1) SEL 18 mg: This group includes all subjects who received SEL 18 mg in the Randomized Phase.
- 2) SEL 6 mg: This group includes all subjects who received SEL 6 mg in the Randomized Phase.
- 3) SEL Pooled: This group includes all subjects who received SEL 18 mg or SEL 6 mg in the Randomized Phase.
- 4) Placebo: This group includes all subjects who received only placebo in the Randomized Phase.

Open-Label Phase (only OL Phase data will be summarized for this group):

OL SEL 18 mg: This group includes all subjects who received OL study drug.

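### Week 240 adverse-event tables use crude percentages from the Randomized Phase only, so AEs with continuing risk are compared over follow-up that depends on efficacy

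*SAP*

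**What the plan says.** SAP 7.1.6 defines the adverse-event summaries: "The number and percentage of subjects who experienced at least 1 TEAE will be provided and summarized by SOC, HLT and PT". The counting rule is "Multiple events will be counted only once per subject in each summary". Neither SAP 7.1.6 nor Protocol 8.8.2 uses person-time or an exposure-adjusted rate.

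Three rules fix how long a subject is observed in these tables:

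- SAP 3.2, for the randomized safety groups: "only Randomized Phase data will be summarized for these groups".
- SAP 7.1.5.1 counts an event as treatment-emergent if its onset is "no later than 30 days after permanent discontinuation of study drug in the Randomized Phase" and before any first open-label dose. AEs that lead to premature discontinuation of study drug also count.
- Protocol 3.3.1 states that after adjudication of a hepatic event "the subject will no longer participate in the Randomized Phase". The condition attached to this exit excepts biopsy-proven cirrhosis, but Protocol 6.7 offers open-label rollover to "Subjects who progress to cirrhosis on liver biopsy or experience a hepatic clinical event". SAP 4.1 has a disposition category for subjects whose randomized drug ended because of a clinical event.

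On frequency, SAP 1.3 says "The estimate of the expected event rate is 30% in untreated patients" and assumes 16.3% on SEL (hazard ratio 0.50), with 20% dropout.

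Two provisions bear on unequal follow-up. Duration of exposure is tabulated by group (SAP 4.2.1), and adjudicated cardiovascular events get Kaplan-Meier estimates and a hazard ratio (SAP 7.1.7.1).

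**The concern.** A crude percentage compares arms fairly only if they are observed for similar lengths of time. Here an efficacy event can close the observation window, and the plan assumes half the hazard of such events on SEL. If SEL works as assumed, its subjects stay in the Randomized Phase longer and have more time to report any AE whose risk continues. The tables would then show an excess on SEL that reflects follow-up and not toxicity.

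Safety and tolerability is the only secondary objective (Protocol 2). By the testing rule in Protocol 8.4, the trial reaches Week 240 only if at least one SEL arm has succeeded on histology. The long-term tables would therefore be read in the setting where follow-up may differ by arm. The SAP allows for follow-up time in one safety outcome, cardiovascular events, but not in TEAEs, Grade 3 or higher TEAEs or SAEs.

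**Working it through.** **Inputs** (SAP 1.3): 240 weeks; EFS events 30% on placebo; hazard ratio 0.50; dropout 20%; 320 subjects per SEL arm and 160 on placebo.

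**The plan's own figures first.** SEL event-free rate = 0.70^0.5 = 0.837, as stated. Events for one comparison = 160 × 0.30 + 320 × 0.1633 = 48.0 + 52.3 = 100.3. Schoenfeld power at two-sided 0.025 = Φ(√(100.3 × 1/3 × 2/3) × ln 2 − 2.241) = Φ(1.03) = 84.9%, against 85% stated. This version ignores dropout. With dropout as a competing exit there are 90.3 events; Schoenfeld gives 80.6%, and a variance of 1/d0 + 1/d1 gives 85.3%. The inputs are therefore the plan's.

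**Mean Randomized Phase exposure.** Assume exponential times and that every EFS event ends exposure. Weekly hazards:

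- placebo event: −ln(0.70)/240 = 0.001486
- SEL event: half of that, 0.000743
- dropout: −ln(0.80)/240 = 0.000930

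Mean exposure = (1 − exp(−240k))/k, where k = event hazard + dropout hazard.

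- Placebo: (1 − 0.70 × 0.80)/0.002416 = 182.1 weeks
- SEL: (1 − 0.837 × 0.80)/0.001673 = 197.7 weeks
- Ratio 1.085. Without dropout: 201.9 and 219.8 weeks, ratio 1.089.

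**Crude percentage for an AE with equal constant hazard h in both arms.** Crude % = h/(h + k) × (1 − exp(−240(h + k))), with h set by the true 240-week risk and 20% dropout. The standard error (SE) of the difference uses 160 and 320 subjects.

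| True risk | Placebo | SEL | Ratio | Difference (points) | SE (points) |
|---|---|---|---|---|---|
| 10% | 7.63% | 8.27% | 1.084 | 0.6 | 2.6 |
| 20% | 15.3% | 16.6% | 1.082 | 1.3 | 3.5 |
| 40% | 31.1% | 33.5% | 1.077 | 2.4 | 4.5 |

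Under this model the first-event rate per unit of time at risk is identical in the two arms (ratio 1.00).

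**Sensitivity to exit timing.** Scheduled biopsies fall at Weeks 48 and 240. Without dropout, if a share f of EFS exits falls at Week 48 and the rest at Week 240, mean exposure = 240 − p × f × 192, with p = 0.30 on placebo and 0.163 on SEL.

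- f = 0: 240 and 240 weeks, ratio 1.00
- f = 0.5: 211.2 and 224.3 weeks, ratio 1.06
- f = 1: 182.4 and 208.6 weeks, ratio 1.14

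**Where the gap shrinks or reverses.**

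- Week 48 analysis, no dropout: 46.3 and 47.2 weeks, ratio 1.018.
- A 20% AE confined to the first 12 weeks, with dropout: crude 19.7% and 19.8%.
- Discontinuation: if SEL dropout were about 33% and placebo dropout stayed at 20%, mean exposure would be equal. A higher figure would reverse the gap.

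**The constant rate has its own bias.** For the same early AE, first-event time at risk averages 146.8 weeks on placebo and 159.3 on SEL. With 5,217.9 weeks in 100 years, the rates are 0.1972/146.8 × 5,217.9 = 7.0 and 0.1981/159.3 × 5,217.9 = 6.5 per 100 subject-years. The ratio is 0.926, a false reduction of about 7% on SEL.

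**The case against.** The strongest case for leaving the plan alone has five parts.

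1. The AE tables are descriptive, with no AE test described, and each difference above is well under one standard error.
2. Exposure is tabulated by arm, so an imbalance would be visible.
3. Under the plan's assumptions the distortion works against SEL, so it would not hide harm.
4. The compulsory exit in Protocol 3.3.1 excepts histological cirrhosis, and rollover for those subjects is only offered. That component may be the largest. Protocol 1.4.1 cites 14% liver-related events in F3 over a median 12.6 years, against 30% composite events assumed in 240 weeks (about 4.6 years). Cirrhosis first found at the Week 240 biopsy costs no exposure.
5. Constant rates would bring in an error of similar size for early AEs.

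Points 1, 4 and 5 stand; they limit the size of the problem and shape the fix. Point 2 stands only in part: total exposure does not give time at risk to first event for each AE. Point 3 depends on discontinuation. In earlier studies in other diseases, drug discontinuation was 28.9% on SEL 18 mg against 22.4% on placebo (diabetic kidney disease, Protocol 1.2.4.1) and 36.0% against 13.5% (alcoholic hepatitis, Protocol 1.2.6.2). A similar imbalance here would shorten SEL observation and could mask harm. Crude percentages cannot distinguish these situations. A small shift in one direction across many AEs can also look like a consistent pattern, even when no single AE stands out.

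A reader might infer that a working drug would show more of every AE and SAE. The documents do not support that. Early AEs hardly move. Ascites, encephalopathy, portal-hypertensive bleeding and death are EFS components (SAP 6.2.1) that SEL is assumed to reduce, and SAP 6.2.3 already analyses the composite by time to event.

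**Conclusion.** The point holds in a limited form and is a desirable improvement, not a fault in a confirmatory analysis. At Week 240, for non-hepatic AEs whose risk continues through follow-up, the planned percentages would show about 8% relative excess on SEL when the true hazards are equal. The exposure ratio behind this is 1.085 with exponential exits and 20% dropout in both arms. Without dropout it runs from 1.00 (all exits at the Week 240 biopsy) to 1.14 (all at the Week 48 biopsy). The Week 48 analysis (about 1.02) and early-onset AEs are little affected, and progression-related AEs should move the other way.

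The figures rest on assumptions that the documents do not give: exponential event, dropout and AE times; AE risk independent of the EFS event; every EFS event ending Randomized Phase exposure; and no allowance for the 30-day tail. They also assume that the plan's hazard ratio of 0.50 is real and that dropout is equal. It would be going too far to conclude that rates should replace percentages, since they would understate early AEs in the arm with longer exposure.

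**What to change.** In SAP 7.1.6, keep the crude percentages as planned. For the Week 240 analysis, add beside them, for all TEAEs, Grade 3 or higher TEAEs, treatment-related TEAEs and SAEs:

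- Kaplan-Meier cumulative incidence by randomized arm, the method already planned for cardiovascular events in SAP 7.1.7.1; and/or
- first-event rates per 100 subject-years at risk, with rate differences between each SEL arm and placebo.

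Do not make constant rates the main comparison. State in the SAP that they dilute early-onset AEs in the arm with longer exposure (about 7% in favour of SEL for an AE confined to the first 12 weeks), and that both additions treat exit from the Randomized Phase as unrelated to AE risk.

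The cost is SAP wording and a few table columns. No new data are needed and no confirmatory test changes.
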